#### **14.1.2 Unanticipated Problem Reporting**

The investigator will report unanticipated problems (UPIRTSOs) to the reviewing Institutional Review Board (IRB) and to the Data Coordinating Center (DCC)/lead principal investigator (PI). The UPIRTSO report will include the following information:

- Protocol identifying information: protocol title and number, PI's name, and the IRB project number;
- A detailed description of the event, incident, experience, or outcome;
- An explanation of the basis for determining that the event, incident, experience, or outcome represents an UPIRTSO;
- A description of any changes to the protocol or other corrective actions that have been taken or are proposed in response to the UPIRTSO.

To satisfy the requirement for prompt reporting, UPIRTSOs will be reported using the following timeline:

- UPIRTSOs that are serious adverse events (SAEs) will be reported to the IRB and to the DCC/study sponsor within <insert timeline in accordance with policy> of the investigator becoming aware of the event.
- Any other UPIRTSO will be reported to the IRB and to the DCC/study sponsor within <insert timeline in accordance with policy> of the investigator becoming aware of the problem.
- All UPs should be reported to appropriate institutional officials (as required by an institution's written reporting procedures), the supporting agency head (or designee), Food and Drug Administration (FDA), and the Office for Human Research Protections (OHRP) within <insert timeline in accordance with policy> of the IRB's receipt of the report of the problem from the investigator.

## **15. Data and Safety Monitoring Plan (DSMP)**

*Weill Cornell Medicine Data and Safety Monitoring Committee (WCM DSMC) will be composed of medical and statistical independent reviewers and will meet to review the efficacy and safety data and determine a risk/benefit analysis in this subject population. The purpose of the WCM DSMC is to advise on serious safety considerations, lack of efficacy and any other considerations within the charge to the Committee. The WCM DSMC may request additional meetings or safety reports as deemed necessary upon discussion with Karyopharm Therapeutics and its representatives. The PI, [name], will be the safety contact for all WCM DSMC related analysis outcomes and can be contacted at:*

Weill Cornell Medicine Myeloma Center  
[name]  
[name]  
[contact]  
[contact]  
Email: [contact]

The WCM DSMC may stop the study following review of results from each interim analysis. The first interim analysis will take place 3 months after the study begins subject accrual or after 6 patients have been enrolled, whichever occurs first, and will examine the safety and tolerability of minimum one cycle of study treatment prior to enrolling additional subjects. A subsequent interim analysis will take place 6 months after the study begins subject accrual or after 12 patients have been enrolled, whichever occurs first, and every six months thereafter, and will examine both safety and efficacy. The WCM DSMC will also review the study at the end of the first stage of accrual (18 patients) including toxicity data, protocol adherence, and protocol deviations. Efficacy and safety data summaries will be provided to the WCM DSMC after each interim analysis.

Early discontinuation of the study may result from the following study-terminating events:

1. Any abrupt or unexpected patient death that appears to be related to study medication.
2. Early death (defined by death within 30 days of beginning therapy) of more than 50% of subjects at any interim analysis.

3. Early need for hospitalization (defined by hospitalization within 30 days of beginning therapy) of more than 50% of subjects at any interim analysis.
4. Unacceptable toxicity (defined by a Grade 4 or higher drug-related adverse event) in more than 50% of subjects at any interim analysis.
5. The interim stopping rule for the study is defined by statistical futility of the ClaSPD regimen, as outlined in the two-stage study design.

The WCM DSMC will submit their comments/review to the IRB at the time of continuing review and to participating sites upon receipt of review comments.

Written documentation will be provided to investigators and regulatory agencies if the protocol is stopped or paused for toxicity concerns.

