#### **2.4.1.4 Selinexor in combination with pomalidomide and dexamethasone**

The preliminary results of a phase 1b/2 clinical trial reported the most common AEs ( $\geq 20\%$ ) suspected to be related to once-weekly selinexor in combination with pomalidomide and dexamethasone to be neutropenia (67%), thrombocytopenia (52%), nausea (52%), fatigue (52%), anemia (45%), weight loss (39%), anorexia (36%), leukopenia (36%), vomiting (27%), diarrhea (24%), hyponatremia (21%) and dizziness (18%). Most of these effects can be managed effectively with dose modification and/or supportive care initiated prior to first dosing. There were three grade 5 adverse events: one intracranial hemorrhage in cycle 2; one febrile neutropenia in cycle 1 and one pneumonia in cycle 5.

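### Section 15 uses one uncalibrated over-half stopping line for early death, early hospitalisation and Grade 4 or higher toxicity; for early death it is close to inert

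*Combined protocol and SAP*

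**What the plan says.** The stopping provisions are in Section 15 (Data and Safety Monitoring Plan). They open with "Early discontinuation of the study may result from the following study-terminating events" and list five items.

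- Item 1: "Any abrupt or unexpected patient death that appears to be related to study medication".
- Item 2: "Early death (defined by death within 30 days of beginning therapy) of more than 50% of subjects at any interim analysis".
- Item 3: "Early need for hospitalization (defined by hospitalization within 30 days of beginning therapy) of more than 50% of subjects at any interim analysis".
- Item 4: "Unacceptable toxicity (defined by a Grade 4 or higher drug-related adverse event) in more than 50% of subjects at any interim analysis".
- Item 5 is the futility rule of the two-stage design.

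The first look comes at 3 months or "after 6 patients have been enrolled, whichever occurs first"; it covers at least one cycle of treatment and precedes further enrolment. The second comes at 6 months or 12 patients, and later looks follow every six months. There is also a review at 18 patients, the end of stage 1. Beyond the listed items, "The WCM DSMC may stop the study following review of results from each interim analysis", and it may ask for extra meetings or safety reports.

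Section 12.2 gives a type I error rate and power for the efficacy rule. No section gives a target rate, an unacceptable rate, a justification or an operating characteristic for items 2 to 4.

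**The concern.** Three outcomes of very different seriousness share one threshold. A death within 30 days and a drug-related Grade 4 laboratory cytopenia are held to the same line, although their background frequencies are far apart. Over half is far above any early-death rate the documents report, so item 2 could stay silent while a serious problem develops. Three early deaths in the first 6 patients, or nine in 18, would not meet it.

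The protocol itself gives reason to watch early deaths. Section 2.4.1.4 says of selinexor, pomalidomide and dexamethasone: "There were three grade 5 adverse events", one of them in cycle 1. Section 2.4.1.5 reports more treatment-related deaths when clarithromycin was added to lenalidomide and dexamethasone. Those were mostly infections, primarily in patients aged 75 or older, whom this trial excludes. The protocol cites no data on the four drugs together.

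**Working it through.** **Figures to reproduce.** The plan gives none for the safety rules. The only operating characteristics are those of the efficacy rule in Section 12.2. Summing, over stage 1 counts x = 7 to 18, the binomial probability of x in 18 times P(Bin(8, p) ≥ 14 − x) gives power 0.8004 at p = 0.60, matching the stated 0.80. At p = 0.35 it gives 0.0377, within the stated 0.05.

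**Inputs for the safety rules.** Section 15 gives the over-half line and looks at 6, 12 and 18 patients. Section 4.6 gives accrual of 2 per month, so the month-12 look falls at about 2 × 12 = 24 patients.

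**Counts needed.** More than half means floor(n/2) + 1 events: 4 of 6, 7 of 12, 10 of 18, 13 of 24.

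**One look.** The chance of meeting the line is P(Bin(n, p) ≥ floor(n/2) + 1). At n = 6 and p = 0.20:

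15 × 0.2⁴ × 0.8² + 6 × 0.2⁵ × 0.8 + 0.2⁶ = 0.01536 + 0.001536 + 0.000064 = 0.0170.

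At the same true rate it is 0.0039 at n = 12 and 0.0009 at n = 18.

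**All looks together.** An exact recursion carries forward the distribution of the event count among paths that have not yet crossed, adds the next group of patients, and removes the paths that cross. Patients are taken as independent, with complete data at each look.

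| True event rate | Met by look at 6 | Met by look at 12 | Met by look at 18 | With a look at 24 added |
|---|---|---|---|---|
| 10% | 0.13% | 0.13% | 0.13% | 0.13% |
| 20% | 1.7% | 1.9% | 1.9% | 1.9% |
| 30% | 7.0% | 8.7% | 9.3% | 9.5% |
| 33% | 9.7% | 12.4% | 13.4% | 13.9% |
| 40% | 17.9% | 24.2% | 27.4% | 29.3% |
| 50% | 34.4% | 47.8% | 55.4% | 60.5% |
| 60% | 54.4% | 72.9% | 82.0% | 87.4% |

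**Early death (item 2).** Section 2.4.1.4 gives no denominator for its fatal events. If it is the 51 enrolled reported in Section 2.2.1 (an assumption), the cycle 1 figure is 1/51 = 2.0% and the overall figure 3/51 = 5.9%; a smaller denominator would raise both. A true 20% early-death rate would be about ten times the cycle 1 figure, and item 2 would miss it about 98% of the time.

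**Hospitalisation (item 3).** The same table applies. The documents give no background rate.

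**Grade 4 or higher (item 4).** Section 2.2.1 reports 33% Grade 4 thrombocytopenia alone under selinexor 80 mg twice weekly with dexamethasone, a different schedule. Around that level the line fires 13% of the time; at 40%, 50% and 60% it fires 27%, 55% and 82% of the time (looks to 18).

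**What item 1 adds.** If a fraction q of patients had a qualifying death, the chance of at least one is 1 − (1 − q)ⁿ. For q = 5%: 1 − 0.95⁶ = 26% by 6 patients and 1 − 0.95¹⁸ = 60% by 18. For q = 10%: 47% and 85%.

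**Contrast, for arithmetic only.** If 5% early death were taken as tolerable, a boundary of 2/6, 3/12, 4/18, 4/24 (each look at or below a 5% binomial tail) would be crossed with probability 5.9% at a true 5%, 77% at 20% and 96% at 30%. The 5% is not in the documents and is not a recommendation.

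**Slower accrual.** The first look may come at 3 months with fewer than 6 patients. With 3, the line is 2 of 3, met at a true 20% with probability 3 × 0.2² × 0.8 + 0.2³ = 10.4%, and at a true 10% with probability 3 × 0.1² × 0.9 + 0.1³ = 2.8%. How strict the rule is then depends on the pace of enrolment, not on any tolerable rate.

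**The case against.** The strongest reply is that items 2 to 4 are backstops. An independent medical and statistical committee reviews the data on a schedule, may stop after any interim analysis, and has a safety review at 6 patients before more are enrolled. Item 1 makes one abrupt or unexpected, apparently drug-related death enough to consider stopping. Nine early deaths in 18 could pass without consequence only if none met item 1 and the committee did nothing at 6 and 12 patients.

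Most of this stands, and it rules out some stronger readings:

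- A reader might infer that the safety rules give no real protection, or that stopping rests wholly on unplanned judgement. The documents do not support that: item 1 exists and the reviews are scheduled. Only the numerical criteria for using discretion are missing.
- A reader might infer that there is no run-in. None is so named, but the six-patient review before further enrolment does much of that work.
- A reader might infer that all three lines almost never fire. For Grade 4 or higher events that is wrong at plausible unsafe rates.
- A reader might describe this as the first use of the four drugs together. The protocol cites no earlier four-drug data, but does not say that none exist.

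The reply does not rescue the early-death line. Item 1 leaves out deaths judged expected or unrelated to study drug, such as an infectious death attributed to the disease, and committee discretion has no rate to work against.

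**Conclusion.** The point stands in this form: items 2 to 4 share one uncalibrated line, with no stated tolerable rate or operating characteristics. For early death the line is close to inert (1.9% chance of being met at a true 20%, 9.3% at 30%, looks at 6, 12 and 18), so effective protection comes from item 1 and committee discretion. For hospitalisation the behaviour is the same up to about 30%. For Grade 4 or higher events the line fires but separates poorly: 13% at a rate the documents already report for one Grade 4 toxicity, and only 27% at 40%.

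The figures assume independent patients, complete 30-day data at each look, accrual near 2 per month, and the 18-patient review counting as an interim analysis. Slower accrual makes the first look smaller and the line easier to meet. What counts as unsafe is not in the documents, so a range of true rates is shown.

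**What to change.** In Section 15, replace the common line in items 2 to 4 with a separate count boundary for each event type. Derive each by an exact sequential or beta-binomial calculation from a tolerable rate that the committee sets for that event. Tabulate the counts and the crossing probabilities, at the tolerable rate and at higher rates, for the planned looks at 6, 12, 18 and about 24 patients, and give the rule for a calendar look that falls at another number. State that crossing a boundary pauses accrual for committee review. A boundary at 26 would have no accrual left to pause. Keep item 1 as it is.

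The cost is a short calculation, some wording, and a small chance of an unneeded pause, to be stated for each event type. A boundary cannot be carried from one event to another: one of 3/6, 4/12, 5/18, built for a 10% tolerable rate, would be crossed 4.6% of the time at 10% but 79% of the time at a true 33%.

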## 17. Appendices

### Appendix 1. Cytochrome P450 Drug Interactions

#### Inducers

1A2	2B6	2C8	2C9	2C19	2D6	2E1	3A457
beta-naphthoflavone	artemisinin	rifampin	carbamazepine	carbamazepine	dexamethasone	ethanol	barbiturates
broccoli	carbamazepine		enzalutamide	efavirenz	rifampin	isoniazid	brigatinib
brussel sprouts	efavirenz		nevirapine	enzalutamide			carbamazepine
carbamazepine	nevirapine		phenobarbital	norethindrone			efavirenz
char-grilled meat	phenobarbital		rifampin	not pentobarbital			enzalutamide
insulin	phenytoin		secobarbital	prednisone			glucocorticoids
methylcholanthrene	rifampin		st. john's wort	rifampicin			modafinil
modafinil				ritonavir			nevirapine
naftcilin				st. john's wort			oxcarbazepine
omeprazole							phenobarbital2
rifampin							phenytoin2
rucaparib							pioglitazone
teriflunomide							rifabutin
tobacco							rifampin1
							st. john's wort
							troglitazone1

#### Inhibitors

Inhibitors compete with other drugs for a particular enzyme thus affecting the optimal level of metabolism of the substrate drug which in many cases affect the individual's response to that particular medication, e.g. making it ineffective.

- A **Strong inhibitor** is one that causes a > 5-fold increase in the plasma AUC values or more than 80% decrease in clearance.
- A **Moderate inhibitor** is one that causes a > 2-fold increase in the plasma AUC values or 50-80% decrease in clearance.
- A **Weak inhibitor** is one that causes a > 1.25-fold but < 2-fold increase in the plasma AUC values or 20-50% decrease in clearance.
- **TBD** Inhibitor strength level is under review.

FDA preferred and acceptable inhibitors for in vitro experiments.\*

1A2	2B6	2C8	2C9	2C19	2D6	2E1	3A457
amiodarone■	clopidogrel■	gemfibrozil■	amiodarone■	chloramphenicol■	amiodarone■	■ diethyl-dithiocarbamate2	aprepitant■
cimetidine■	crisaborole■	glitazones■	capecitabine■	cimetidine■	bupropion■		cimetidine■
ciprofloxacin■	rucaparib■	montelukast■	clopidogrel■	citalopram■	cimetidine■	disulfiram■	clarithromycin■
citalopram■	thiotepe■	quercetin■	crisaborole■	esomeprazole■	cinacalcet■	ribociclib■	diltiazem■
crisaborole■	ticlopidine■	teriflunomide■	efavirenz■	felbamate■	duloxetine■		erythromycin■
efavirenz■	voriconazole■	trimethoprim■	fenofibrate■	fluoxetine■	fluoxetine■		fluconazole■
fluoroquinolones■			fluconazole■	fluvoxamine■	paroxetine■		grapefruit juice■
fluvoxamine■			fluvastatin■	indomethacin■	quinidine1■		indinavir■
furanifylline■			fluvoxamine■	isoniazid■	sertraline■		itraconazole1■
interferon■			isoniazid■	ketoconazole■	terbinafine■		ketoconazole■
methoxsalen■			lovastatin■	lansoprazole■	celecoxib■		nefazodone■

1A2	2B6	2C8	2C9	2C19	2D6	2E1	3A457
mibepradii■			metronidazole■	modafinil■	chlorpheniramine■		nelfinavir■
ribociclib■			paroxetine■	omeprazole■	chlorpromazine■		ritonavir■
rucaparib■			phenylbutazone■	oral contraceptives■	citalopram■		saquinavir■
ticlopidine■			probenicid■	oxcarbazepine■	clemastine■		amiodarone■
			rucaparib■	pantoprazole■	clomipramine■		atomoxetine■
			sertraline■	probenicid■	cocaine■		boceprevir■
			sulfamethoxazole■	rucaparib■	diphenhydramine■		chloramphenicol■
			sulfaphenazole■	ticlopidine■	doxepin■		ciprofloxacin■
			teniposide■	topiramate■	doxorubicin■		delavirdine■
			voriconazole■	voriconazole■	escitalopram■		■ diethyl-dithiocarbamate
			zafirlukast■		halofantrine■		esomeprazole■
					haloperidol■		fluvoxamine■
					■ histamine h1 receptor antagonists		gestodene■
					hydroxyzine■		idelalisib■
					levomepromazine■		imatinib■
					methadone■		lesinurad■
					metoclopramide■		mibepradii■
					mibepradii■		mifepristone■
					midodrine■		■ netupitant/palonosetron
					moclobemide■		norfloxacin■
					panobinostat■		norfluoxetine■
					perphenazine■		not azithromycin■
					promethazine■		omeprazole■
					ranitidine■		pantoprazole■
					■ reduced-haloperidol		regorafenib■
					ritonavir■		ribociclib■
					rolapitant■		starfruit■
					rucaparib■		telaprevir■
					ticlopidine■		telithromycin■
					tripelennamine■		verapamil■
							voriconazole■

## Substrates

1A2	2B6	2C8	2C9	2C19	2D6	2E1	3A457
acetaminophen	artemisinin	amodiaquine	amitriptyline	amitriptyline	alprenolol	acetaminophen?	abemaciclib
amitriptyline	bupropion	cerivastatin	capecitabine	atomoxetine	amitriptyline	napqi	acalabrutinib
caffeine	cyclophosphamide	paclitaxel	celecoxib	brivaracetam	amphetamine	aniline	alectinib
clomipramine	efavirenz	repaglinide	clopидogrel	carisoprodol	ariPIPrazole	benzene	alfentanil
clozapine	ifosfamide	selexipag	diclofenac	chloramphenicol	atomoxetine	chlorzoxazone1	alprazolam
cyclobenzaprine	ketamine	sorafenib	doxepin	citalopram	brexpiprazole	enflurane	amitriptyline
doxepin	meperidine	torsemide	fluoxetine	clomipramine	bufuralol	ethanol	amlodipine
duloxetine	methadone		fluvastatin	clopидogrel	cariprazine	halothane	aprepitant
estradiol	nevirapine		glibenclamide	cyclophosphamide	carvedilol	isoflurane	ariPIPrazole
fluvoxamine	propafol		glimepiride	diazepam-nor	chlorpheniramine	methoxyflurane	astemizole
haloperidol	selegiline		glipizide	doxepin	chlorpromazine	n,n-dimethylformamide	atorvastatin
imipramine n-deme	sorafenib		glyburide	escitalopram	citalopram	sevoflurane	boceprevir
mexiletine	tramadol		ibuprofen	esomeprazole	clomipramine	theophylline?8-oh	brexpiprazole
nabumetone	velpatasvir		irbesartan	flibanserin	clonidine		brigatinib
napqi			lesinurad	hexobarbital	codeine		buspirone
naproxen			lornoxicam	imipramine n-deme	codeine (20-desme)		cafergot
olanzapine			losartan	indometacin	debrisoquine		caffeine -tmu
ondansetron			meloxicam	labetalol	desipramine		carbamazepine
phenacetin			nateglinide	lansoprazole	deutetetabenazine		cariprazine
pirfenidone			phenytoin-4-oh2	moclobemide	dexfenfluramine		cerivastatin
propranolol			piroxicam	nelfinavir	dextromethorphan1		chlorpheniramine
riluzole			rosiglitazone	nilutamide	donepezil		cilostazol
ropivacaine			s-naproxen-nor	omeprazole	doxepin		cisapride
rucaparib			s-warfarin1	pantoprazole	duloxetine		citalopram
tacrine			uprofen	phenobarbital	eliglustat		clarithromycin
theophylline			tamoxifen	phenytoin(o)	encainide		clopidogrel
tizanidine			tolbutamide	primidone	escitalopram		cobimetinib
triamterene			tolbutamide1	progesterone	flecainide		cocaine
verapamil			torsemide	proguanil	fluoxetine		codeine
warfarin			valproic acid	propranolol	fluvoxamine		codeine-n-demethylation
zieuton			venlafaxine	r-mephobarbital	haloperidol		copanlisib
zolmitriptan			voriconazole	r-warfarin	ibrutinib		cyclosporine
			zakirlukast	s-mephenytoin	imipramine		daclatasvir
				suvorexant	lidocaine		dapsone
				teniposide			deflazacort
				venlafaxine	methoxyamphetamine		dexamethasone
					metoclopramide		

1A2	2B6	2C8	2C9	2C19	2D6	2E1	3A457
				voriconazole			
					mexiletine		dextromethorphan2
					minaprine		diazepam?3oh
					nebivolol		diltiazem
					netupitant/palonosetron		docetaxel
					nortriptyline		domperidone
					ondansetron		doxepin
					oxycodone		efavirenz
					paroxetine		elbasvir/grazoprevir
					perhexiline		eliglustat
					perphenazine		plererone
					phenacetin		erythromycin2 (not 3a5)
					phenformin		escitalopram
					pimavanserin		esomeprazole
					promethazine		estradiol
					propafenone		felodipine
					propranolol		fentanyl
					risperidone		finasteride
					risperidone?9-oh		flibanserin
					rucaparib		gleevec
					s-metoprolol		haloperidol
					sparteine		hydrocortisone
					tamoxifen		ibrutinib
					tetrabenazine		idelalisib
					thioridazine		indinavir
					timolol		irinotecan
					tramadol		isavuconazonium sulfate
					valbenazine		ivabradine
					venlafaxine		laam
					zuclopentixol		lansoprazole
							lenvatinib
							lercanidipine
							lidocaine
							lovastatin
							methadone
							midazolam1
							naldemedine
							naloxegol
							nateglinide
							nefatinavir
							neratinib
							netupitant/palonosetron
							nevirapine

**1A2**

**2B6**

**2C8**

**2C9**

**2C19**

**2D6**

**2E1**

**3A457**

nifedipine2  
nisoldipine  
nitrendipine  
not azithromycin  
not pravastatin  
not rosuvastatin  
olaparib  
omeprazole  
ondansetron  
osimertinib  
palbociclib  
panobinostat  
pantoprazole  
pimavanserin  
pimozide  
progesterone  
propranolol  
quetiapine  
quinidine?3-oh (not 3a5)  
quinine  
regorafenib  
ribociclib  
risperidone  
ritonavir  
rolapitant  
romidepsin  
salmeterol  
saquinavir  
selexipag  
sildenafil  
simvastatin  
sirolimus  
sonidegib  
sorafenib  
sunitinib  
suvorexant  
tacrolimus  
tacrolimus(fk506)  
tamoxifen  
taxol  
telaprevir  
telithromycin  
terfenadine  
testosterone1

1A2	2B6	2C8	2C9	2C19	2D6	2E1	3A457
							torisel
							tramadol
							trazodone
							valbenazine
							velpatasvir
							vemurafenib
							venetoclax
							venlafaxine
							verapamil
							vincristine
							voriconazole
							zaleplon
							ziprasidone
							zolpidem

Source: Flockhart DA. Drug Interactions: Cytochrome P450 Drug Interaction Table. Indiana University School of Medicine (2007). "<https://drug-interactions.medicine.iu.edu>" Accessed 01/20/2020.

## Appendix 2. Glutathione (GSH)-, S-adenosylmethionine (SAM)-, or N-acetylcysteine (NAC)-Containing Products

Glutathione (GSH)		S-adenosylmethionine (SAM)		N-acetylcysteine (NAC)	
Product Name	Ingredient	Product Name	Ingredient	Product Name	Ingredient
Glutathione	glutathione	Acetadote for acetaminophen overdose	acetylcysteine	SAM-e Complete	S-adenosylmethionine
L-Glutathione	L-glutathione	Cerefolin NAC: medical food for age-related memory loss	L-methylfolate, vitamin B12, N-acetyl cysteine	SAMe	S-adenosyl-L-methionine
Glutathione reduced	glutathione	NAC	N-acetyl cysteine	Double Strength SAMe 400	S-adenosylmethionine
Reduced glutathione with alpha lipoic acid	Setria L-glutathione	N-A-C Sustain	N-acetyl L-cysteine		
Glutathione, Cysteine & C	Glutathione, L-cysteine, vitamin C	Best NAC Detox Regulators	N-acetyl cysteine		

(Mega-) Liposomal Glutathione	glutathione				
Lypospheric GSH	glutathione				
Ivory Caps Skin Enhancement Formula	glutathione				

